#### **13.2.1.3 Patient Global Impression of Change**

The PGIC will be assessed at Visit 7 through Visit 11. Subjects respond to the question “Since the start of the trial, my overall status is:” with 1 of 7 possible responses (very much improved, much improved, minimally improved, no change, minimally worse, much worse, very much worse). A response of “very much improved” or “much improved” is generally regarded as a clinically important outcome. The response to treatment based on the PGIC will be derived by classifying subjects with outcome “very much improved” or “much improved” as responders, and subjects with other outcomes as non-responders. Subjects with missing PGIC score will be considered as non-responders.

All PGIC scores and the derived responder status will be presented in a subject data listing.

A descriptive summary of the categorical PGIC scores and the responder status will be generated by visit. This includes the summary of the secondary PGIC endpoints at Week 12 and Week 26.

A graphical plot of the distribution of the PGIC will be created by visit.

#### **13.2.1.4 Brief Pain Inventory**

Subjects will complete the brief pain inventory (BPI) Interference Scale questionnaire at Visit 2 and Visit 7 through Visit 11.

The BPI is a multi-item scale measuring the impact of pain on functioning and well-being. The 7 pain interference items: general activity, walking, work, mood, enjoyment of life, relations with others, and sleep, are each rated on a 0 to 10 scale using a 24-hour recall period, with 0 indicating “does not interfere” and 10 indicating “completely interferes”.

The total Pain Interference Score is calculated by adding the scores for the 7 questions and dividing by 7, i.e., the average of the 7 item scores. This gives an interference score with a range from 0 to 10. If not more than 3 of the 7 items are missing, the average is calculated based on the available 4, 5, or 6 item scores. If more than 3 of the 7 items are missing, the total score will not be calculated and is considered missing.

The scale can also be subdivided into activity (general activity, walking, work and sleep) and affective (mood, enjoyment of life, relations with others) subcomponents. For the activity and affective subcomponents, the subcomponent score will not be calculated and is considered missing if 1 of the item scores is missing.

All individual item BPI scores, the subcomponent scores, and the total score will be presented in a subject data listing.

A descriptive summary of the categorical individual item scores will be generated by item and visit. Furthermore, a descriptive summary of the continuous subcomponent scores and the continuous total score, and the corresponding changes from baseline will be generated by score type (subcomponent scores, and the total score) and visit. This includes the summary of the secondary BPI endpoints at Week 12 and Week 26.

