**Handling of missing data**

Missing data will not be imputed in this trial. The number of missing data will be included in all descriptive summaries.

An MMRM will be conducted on the observed values of the change in current pain intensity score. An MMRM leads to unbiased estimates if the missingness mechanism is missing-at-random. Due to the long-acting effect of neridronic acid, missing-at-random is considered a clinically plausible assumption. The MMRM in this trial will include the covariate baseline pain intensity and the factors pooled site and visit as fixed effects, and subject as random effect. An unstructured covariance matrix will be used to model the covariance structure. Least squares means, standard errors, and 95% confidence intervals for the change from baseline will be obtained.

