## 13 EFFICACY ANALYSES

All efficacy data will be analyzed overall, i.e., for the single treatment group neridronic acid 400 mg, for the FAS, unless specified otherwise.

All efficacy data will be presented in subject data listings.

Missing efficacy data will not be imputed in this trial. The number of missing values will be included in all descriptive summaries.

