### 13.2 Secondary endpoints

All secondary efficacy endpoints will be analyzed for the FAS and additionally for the TCS.

The following secondary efficacy endpoints will be analyzed overall and by subgroups:

- Change from baseline to Week 12 and Week 26 in the current pain intensity score, using a numerical rating scale (NRS).
- Response to treatment, defined as at least 30%, at least 50% and at least 2 points on the NRS decrease from baseline in the current pain intensity score, at Week 12 and Week 26.
- Patient Global Impression of Change (PGIC) at Week 12 and Week 26.
- Change from baseline to Week 12 and Week 26 in the Pain Interference score of the Brief Pain Inventory (BPI).

Since this is a single-arm trial, no hypothesis testing of secondary efficacy endpoints between treatment arms is planned. All secondary efficacy endpoints will be analyzed descriptively.

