### **13.2.2 Sensitivity analysis**

Not applicable.

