### **13.3.1 Average and worst pain intensity**

Worst and average pain intensities will be added to the subject data listing of current pain values (see Section 13.2.1.1). The listing will be presented by pain type (average, current, and worst).

Worst and average pain intensities will be added to the descriptive summary of current pain. The summary will be presented by pain type.

Change in the worst pain intensity and average pain intensity for all post-baseline visits will be analyzed using the same statistical model as the one used for the current pain.

Point estimates least square means (LSmeans), standard errors, and 95% CIs for the factor visit in the MMRM model representing the change from baseline at each visit will be presented. Results will be added to the model-based summary of current pain.

Graphical plots of the model-based estimates and the 95% CI of the change from baseline of worst and average pain intensity will be created. The plots will be added to the graphical plots of current pain intensity scores.

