**20.1.1.7 Handling of missing values**

At each time point/visit, all subjects still in the trial are reported. Missing values will be taken into account as missing in the analysis. The number of observed values and the number of missing values must sum up to the number of subjects in the trial at the respective time point/visit.

Missing measurements/missing values are identified by the SDTM variable \*\*STAT=ND. If this variable is not recorded (it's a permissible variable) the missing values of \*\*ORRES should be used.

Unless otherwise specified in the SAP, missing values will not be imputed.

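### The secondary endpoint of change in BPI Pain Interference gets only an observed-case summary, which can overstate the Week 26 improvement if dropout depends on earlier BPI scores

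*SAP*

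**What the plan says.** Protocol 1.2 and SAP 13.2 name change from baseline in BPI Pain Interference at Week 12 and Week 26 as a secondary efficacy endpoint. The BPI is completed at Visit 2 and at Visits 7 to 11.

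For its analysis, SAP 13.2.1.4 says that "a descriptive summary of the continuous subcomponent scores and the continuous total score, and the corresponding changes from baseline will be generated" by score type and visit, and adds: "This includes the summary of the secondary BPI endpoints at Week 12 and Week 26". Four other places bear on this:

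- SAP 13: "Missing efficacy data will not be imputed in this trial".
- SAP 13.2.2, on sensitivity analysis for the secondary endpoints: "Not applicable".
- SAP 20.1.1.7: observed and missing counts "must sum up to the number of subjects in the trial at the respective time point/visit". A subject who has left is therefore counted neither as observed nor as missing.
- SAP 20.1.1.14: data from an early termination visit are moved to a scheduled visit and analysed there.

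For current pain, Protocol 14.1.7 specifies an MMRM on the ground that "An MMRM leads to unbiased estimates if the missingness mechanism is missing-at-random", and judges that assumption plausible because the drug is long-acting. SAP 13.3.1 widens the use of the model: "Change in the worst pain intensity and average pain intensity for all post-baseline visits will be analyzed using the same statistical model" as for current pain. Protocol 1.2 lists worst and average pain among data not considered endpoints.

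**The concern.** An observed-case mean describes the subjects who still have a value at that visit. It estimates the mean for the whole treated set in general only when leaving is unrelated to outcome. The plan's stated reasoning for pain rests on a weaker condition, under which leaving may depend on values already recorded. A likelihood-based repeated-measures model uses those earlier values; the visit mean does not.

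Of the secondary efficacy endpoints, current pain has the MMRM, and pain response and PGIC response count missing as non-response (SAP 13.2.1.1 to 13.2.1.3). BPI change has only item-level scoring rules and the re-assignment of early termination data.

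At stake is a Week 26 functional improvement that may look better than it is, in a trial with no control arm in which such bias could cancel. The same summary is repeated in the Treatment Completers Set and in the CRPS-duration subgroups.

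**Working it through.** **No figure to reproduce.** The sample size of about 290 (Protocol 1.5.1) rests on safety-exposure needs. The documents give no effect size, SD or dropout rate for BPI, so the size of the problem was explored by simulation.

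**Inputs from the documents.** N = 290; BPI visits at Weeks 6, 12 and 26 (Visits 7 to 9); a 1-point minimum clinically important decrease (Protocol 12.4.3).

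**Assumptions not in the documents.**
- Mean changes of −1.5, −1.8 and −2.0 at Weeks 6, 12 and 26; SD 2.0 or 2.5.
- Correlation ρ = 0.6 or 0.8 between adjacent visits, and ρ^1.5 between Weeks 6 and 26.
- Total dropout d by Week 26 of 10, 20 or 30%, split equally over two intervals: h = 1 − (1 − d)^½, which gives 0.051, 0.106 and 0.163 per interval. Nobody leaves before Week 6.
- Leaving depends on the last observed change: logit P(leave) = a + 1.0 × z, where z is that change in SD units (higher is worse) and a is set to give h. A slope of 0 gives completely random dropout.
- 0, 50 or 100% of leavers attend an early termination visit, whose value counts at the next visit.

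**Estimators compared, 300 runs per scenario.**
- Observed-case: the mean of the values present at the visit.
- Likelihood-based, standing in for the MMRM: m6 is the Week 6 mean; m12 = b0 + b1·m6; m26 = c0 + c1·m6 + c2·m12, with coefficients estimated from subjects observed at the later visit.

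**Overstatement of the Week 26 improvement by the observed-case mean (points), with outcome-dependent dropout.** Each range covers both SDs and both correlations.

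| Dropout by Week 26 | No early termination visits | Half attended | All attended |
|---|---|---|---|
| 10% | 0.11–0.18 | 0.08–0.15 | 0.05–0.09 |
| 20% | 0.20–0.35 | 0.14–0.25 | 0.08–0.17 |
| 30% | 0.29–0.53 | 0.21–0.37 | 0.12–0.26 |

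At Week 12 the overstatement is 0.06 to 0.30 with no early termination visits, 0.03 to 0.13 with half, and within 0.01 of zero with all. Under completely random dropout both estimators are within 0.03 point of the truth. Under outcome-dependent dropout the likelihood-based mean is within about 0.01 point at both visits.

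**Plausibility check.** The overstatement equals the fraction missing times the difference in true mean change between leavers and stayers. With no early termination data, 0.20/0.20 = 1.0 and 0.35/0.20 = 1.75 at 20% dropout, and 0.29/0.30 = 0.97 and 0.53/0.30 = 1.77 at 30%. The table therefore supposes that leavers do about 1.0 to 1.8 points worse than stayers. A smaller difference shrinks the bias in proportion.

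**Why early termination visits help only in part.** Someone who leaves after Visit 7 has that record moved to Visit 8, so Week 12 is filled but Week 26 stays empty.

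**The case against.** The case for leaving the plan alone has several parts.

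- **Early termination data.** A reader might infer that all dropouts vanish from the endpoint. They do not: the early termination visit repeats Visit 11, which includes the BPI, and its data enter a re-assigned visit. This stands, and at full attendance it removes the Week 12 bias. Attendance is only where possible (Protocol 9.3.3.1), and Week 26 is not fully repaired.
- **Missing at random does not imply bias.** A reader might infer that the summary is biased under the plan's own assumption. Completely random dropout is a special case with no bias. The assumption is also stated for current pain, not for BPI, although the reason given is not specific to a pain score. Treated subjects are encouraged to stay (Protocol 9.3.1), so dependence on outcome may be weak.
- **Comparability with pain.** A reader might infer that BPI cannot be set beside the pain result. SAP 13.2.1.1 also plans an observed-case table for current pain, which is directly comparable.
- **No breach of the protocol.** The protocol requires the MMRM only for current pain and keeps other efficacy analyses descriptive unless stated otherwise. Worst and average pain share the current-pain scale and visits, and the other questionnaires are also summarised descriptively, so the split is largely by instrument. This explains the choice. It does not show that BPI, a secondary endpoint, is better served by the simpler summary.
- **Interval.** SAP 20.1.1.2 shows a confidence interval for the mean as a bracketed item, but neither SAP 8.1 nor 13.2.1.4 calls for one for BPI.
- **The simulation suits the model.** All dropout comes after Week 6 and is missing at random by construction. If leaving depends on unobserved values, the MMRM is not protected either.

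**Conclusion.** The point holds as a weakness in the choice of analysis, of minor to moderate severity. The observed-case summary can overstate the Week 26 BPI improvement when dropout depends on earlier BPI. Under the assumptions listed, the overstatement is 0.05 to 0.53 point depending on dropout and early termination attendance; the upper end is about half the 1-point minimum important decrease. The range rests on an assumed, fairly strong dependence of dropout on outcome, and falls to about zero without it.

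The documents do not support saying that the endpoint is certainly biased, or that the SAP contradicts the protocol. All analyses are exploratory and no inferential test is planned (Protocol 14.1.2). That limits the consequence but does not remove the gain from a better estimate.

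**What to change.** In SAP 13.2.1.4, add an MMRM for change from baseline in the BPI total interference score at Visits 7 to 11, with baseline BPI, pooled site and visit as fixed effects and an unstructured within-subject covariance. Leave out the random subject effect that SAP 13.2.1.1 includes; it is redundant beside an unstructured matrix. Report the Week 12 and Week 26 LS means with 95% CIs as the endpoint estimates. Keep the descriptive table, preferably with the number of subjects who left before each visit.

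The cost is SAP wording and a few more runs of an existing type of model (FAS, TCS and subgroups), with no new data. One limit remains: subjects with no BPI value at Visits 7 to 11 contribute nothing to a change-from-baseline model. That includes anyone whose early termination record is moved to a visit before Visit 7, where the BPI is not scheduled.

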### **13.2.2 Sensitivity analysis**

Not applicable.

### **13.2.3 Other analysis**

Not applicable.

## **13.3 Analysis of other efficacy data**

The following outcome parameters based on other efficacy data collected in this trial will be analyzed for the FAS:

- Change from baseline to Week 12 and Week 26 in the worst pain intensity score, using an 11-point NRS.
- Change from baseline to Week 12 and Week 26 in the average pain intensity score, using an 11-point NRS.
- Change from baseline to Week 12 and Week 26 in the Pain Disability Index (PDI) score.
- Change from baseline to Week 12 and Week 26 in the EuroQoL-5 dimension 5 level (EQ-5D-5L) index score and the health-related visual analog scale (VAS) score.
- Change from baseline to Week 12 and Week 26 in the Pain Anxiety Symptom Scale (PASS) score.
- Change from baseline to Week 12 and Week 26 in the Center for Epidemiological Studies Depression Scale (CES-D) score.
- Change from baseline to Week 12 and Week 26 in the CRPS Severity Score.

### **13.3.1 Average and worst pain intensity**

Worst and average pain intensities will be added to the subject data listing of current pain values (see Section 13.2.1.1). The listing will be presented by pain type (average, current, and worst).

Worst and average pain intensities will be added to the descriptive summary of current pain. The summary will be presented by pain type.

Change in the worst pain intensity and average pain intensity for all post-baseline visits will be analyzed using the same statistical model as the one used for the current pain.

Point estimates least square means (LSmeans), standard errors, and 95% CIs for the factor visit in the MMRM model representing the change from baseline at each visit will be presented. Results will be added to the model-based summary of current pain.

Graphical plots of the model-based estimates and the 95% CI of the change from baseline of worst and average pain intensity will be created. The plots will be added to the graphical plots of current pain intensity scores.

### **13.3.2 Pain Disability Index score**

The PDI questionnaire will be completed by all subjects at Visit 2 and Visit 7 through Visit 11.

The PDI questionnaire includes questions related to pain-related disability in 7 categories: family/home responsibilities, recreation, social activity, occupation, sexual behavior, self-care, and life-support activities. For each of the 7 categories, the subjects are asked to rate on an 11-point NRS the level of disability they typically experience. The PDI is calculated as the sum of the 7 categories, for a minimum value of 0 and maximum value of 70. If one of the 7 items is missing the PDI score will not be calculated and is considered missing.

All individual PDI categories and the total score will be presented in a subject data listing.

A descriptive summary of the categorical individual category scores will be generated by visit. Furthermore, a descriptive summary of the continuous total score and the corresponding changes from baseline will be generated by visit. This includes the summary of the PDI score at Week 12 and Week 26.

### **13.3.3 EuroQoL-5 dimension 5 level score and VAS**

The EQ-5D-5L health questionnaire will be completed by all subjects at Visit 2 and Visit 7 through Visit 11.

The EQ-5D-5L has 5 dimensions: mobility, self-care, usual activities, pain/discomfort, and anxiety/depression. Each of the 5 dimensions has 5 possible levels: no problems, slight problems, moderate problems, severe problems, and extreme problems.

The health state of the subject is coded by the vector of the reported levels in each of the 5 dimensions. An EQ-5D-5L Health Status Index will be derived from the 5-dimensional health status vector using a lookup table that can be downloaded from the website of the EuroQol group. The index set provided for the US in the spread sheet “EQ-5D-5L value sets” of the Excel file “EQ-5D-5L\_Crosswalk\_Value\_Sets.xls” will be used to assign an index value to the health status vector of a subject. For the US general population, the possible EQ-5D-5L index scores range from -0.109 for the health status vector “55555” to 1.0 for the vector “11111” on a scale where an index value of 0.0 represents death and 1.0 represents perfect health.

The EQ-VAS ranges from 0 (worst imaginable health) to 100 (best imaginable health).

All five EQ-5D-5L dimensions, the EQ-5D-5L index, and the EQ VAS will be presented in a subject data listing.

A descriptive summary of the 5 categorical EQ-5D-5L dimensions will be generated by dimension, and visit. Furthermore, a descriptive summary of the continuous EQ-5D-5L index and the EQ VAS, and the corresponding changes from baseline will be generated by visit. This includes the summary of the EQ-5D-5L index and the EQ VAS at Week 12 and Week 26.

### **13.3.4 Pain Anxiety Symptom Scale**

The PASS questionnaire will be completed by all subjects at Visit 2 and Visit 7 through Visit 11.

The PASS questionnaire consists of 20 items designed to assess 4 aspects of pain-related anxiety: cognitive anxiety, escape-avoidance behaviors, fear of pain, and physiological symptoms of anxiety. Subjects rate each item in terms of frequency, from 0 (never) to 5 (always). The total score is calculated as the sum of ratings, with values ranging from 0 to 100; higher scores indicate higher levels of pain-related anxiety. If 1 of the 20 items is missing, the total score will not be calculated and is considered missing. A similar rule is applied to missing items in the calculation of the subcomponents. The subcomponents are defined in terms of the following item subsets ([McCracken and Dhingra 2002](#)):

- Cognitive anxiety: items 5, 10, 14, 17, and 19.
- Escape-avoidance behaviors: items 3, 6, 8, 11, and 20.
- Fear of pain: items 1, 2, 9, 13, and 16.
- Physiological symptoms of anxiety: items 4, 7, 12, 15, and 18.

All individual item PASS scores, the subcomponent scores, and the total score will be presented in a subject data listing.

A descriptive summary of the categorical individual item scores will be generated by visit. Furthermore, a descriptive summary of the 4 continuous subcomponent scores, the continuous total score, and the corresponding changes from baseline will be generated by visit. This includes the summary of the PASS total score at Week 12 and Week 26.

### **13.3.5 Center for Epidemiological Studies Depression Scale score**

The CES-D questionnaire will be completed by all subjects at Visit 2 and Visit 7 through Visit 11.

The 20 items of the scale are symptoms associated with depression. Subjects are asked to rate each item from “rarely or none of the time (less than 1 day)” to “most or all of the time (5 to 7 days)” during the last week. Response scores for all questions except 4, 8, 12, and 16 are: <1 day = 0; 1-2 days = 1; 3-4 days = 2; 5-7 days = 3. For question 4, 8, 12, and 16, the scoring is reversed, i.e., <1 day = 3; 1-2 days = 2; 3-4 days = 1; 5-7 days = 0. The total CES-D score is calculated as the sum of scores for all 20 questions and has a range of 0 to 60. If of the 20 items is missing, the CES-D score will not be calculated and is considered missing.

All individual CES-D items and the total score will be presented in a subject data listing.

A descriptive summary of the categorical individual item scores will be generated by visit. Furthermore, a descriptive summary of the continuous total score and the corresponding changes from baseline will be generated by visit. This includes the summary of the CES-D total score at Week 12 and Week 26.

### **13.3.6 Complex Regional Pain Syndrome Severity Score**

Signs and symptoms of CRPS will be assessed by the investigator at Visit 1 (enrollment), at Visit 2 (baseline) and Visit 7 through Visit 11 and recorded using the electronic patient reported outcome system.

The investigator examines the signs. The subjects are asked to report their symptoms with a recall period of 48 hours. At the Enrollment Visit, subjects are additionally asked to report their symptoms with a recall period since onset of disease for purposes of establishing the diagnosis of CRPS. This information is also used, in combination with the investigators assessment of signs of CRPS at

Visits 9, 10 and 11, to determine whether or not the subject continues to meet criteria for a diagnosis of CRPS at these latter visits ([Table 2](#)).

Table 2: Assessments of CRPS signs and symptoms

	Enrollment	Baseline	Post-baseline
	Visit 1	Visit 2	Visit 7 – Visit 11
Symptoms (recall period since onset) a	X		(X c )
Symptoms (recall period 48 hours) b	X	X	X
Signs	X	X	X

a) Used for establishing the diagnosis of CRPS.

b) Used for CRPS severity score.

c) Values copied from Visit 1.

CRPS = complex regional pain syndrome.

Subjects will be queried on 8 self-reported symptoms (queried YES or NO):

1. Continuing, disproportionate pain.
2. Allodynia and/or hyperalgesia.
3. Temperature asymmetry.
4. Skin color asymmetry.
5. Sweating asymmetry.
6. Edema.
7. Dystrophic changes.
8. Motor abnormalities.

Moreover, subjects will be examined for 8 signs (observed on examination, queried YES or NO):

9. Hyperalgesia to pinprick.
10. Allodynia.
11. Temperature asymmetry by palpation.
12. Skin color asymmetry.
13. Asymmetric edema.
14. Sweating asymmetry.
15. Dystrophic changes.
16. Motor abnormalities.

Each sign or symptom is assigned a dichotomous value (1 = YES/presence; 0 = NO/absence). To derive the CRPS severity score, the symptoms reported with recall period 48 hours and the signs will be added. The resulting CRPS severity score ranges from 0 to 16. If the value for 1 of the

16 signs and symptoms is missing, the CRPS severity score will not be calculated and is considered missing.

The presence of CRPS at post-baseline Visits 7 to Visit 11 will be derived based on the “Budapest clinical diagnostic criteria” (Harden et al. 2010). For the Budapest criteria to be fulfilled, 3 criteria must be verified. The criteria are linked to the symptoms with recall period since onset and the signs in the following way:

1. Criterion (1): question 1 answered YES
2. Criterion (2): at least 3 of the following 4 symptom categories must be fulfilled:
  - Sensory: question 2 answered YES
  - Vasomotor: question 3 or question 4 answered YES
  - Sudomotor/edema: question 5 or question 6 answered YES
  - Motor/trophic: question 7 or question 8 answered YES
3. Criterion (3): at least 2 of the following 4 sign categories must be fulfilled
  - Sensory: question 9 or question 10 answered YES
  - Vasomotor: question 11 or question 12 answered YES
  - Sudomotor/edema: question 13 or question 14 answered YES
  - Motor/trophic: question 15 or question 16 answered YES

A subject data listing will present for:

- The individual signs and symptoms values (YES/NO).
- The answers to follow-up questions in case a sign or symptom is present.
- The CRPS severity score.
- The presence/absence of CRPS (Visits 7 through Visit 11).
- Comments.

A descriptive summary will be created by sign/symptom and visit for:

- The dichotomous symptoms and signs,
- The dichotomous CRPS assessment (present/absent).

For the Enrollment Visit, symptoms with recall period since onset and symptoms with recall period 48 hours will both be summarized. A graphical display of the proportion of affected subjects over the entire 12-month trial period will be created including:

- The proportion of subjects with a sign/symptom, for each of the symptoms with recall period 48 hours and for each of the signs.
- The proportion of subjects meeting the diagnosis of CRPS, i.e., with CRPS presence.

Furthermore, a descriptive summary of the continuous CRPS severity score and the corresponding change from baseline will be generated by visit. A graphical plot of the means and 95% CI of the CRPS severity score over the entire 12-month trial period will be created.

